# **U** NOVARTIS

## **Oncology Global Medical Affairs**

## Non-Interventional Study Protocol (PASS)

## CBYL719C2005

## REDACTED PROTOCOL

| Title                            | Survey among healthcare professionals treating patients with
metastatic breast cancer in selected European countries to
evaluate their knowledge on management of hyperglycemia
when using alpelisib |
|----------------------------------|---|
| Protocol version identifier      | v00   |
| Date of last version of protocol | 08-Jun-2021   |
| EU PAS register
number        | Study not registered  |
| Active substance                 | Alpelisib (ATC code L01XX65)  |
| Medicinal product                | Piqray ® (alpelisib)   |
| Product reference                | EU/1/20/1455/001-009  |
| Procedure
number              | EMEA/H/C/004804   |

| Name of
marketing
authorization
holder(s) | Novartis Europharm Limited   |
|--|--|
| Joint PASS   | No   |
| Research
question and
objectives             | The objective of this survey is to confirm whether HCPs received
the Piqray educational material, and to assess their knowledge
and behavior around management of hyperglycemia in patients
treated with Piqray   |
| Country (-ies) of study                            | Four to 8 countries from the European Union (EU)/European
Economic Area (EEA). These countries may include Austria,
Luxembourg, Norway, Slovenia, Sweden, and the Netherlands
plus up to 2 additional countries depending on timing and
approval of commercialization of Piqray in additional EU/EEA
countries. |
| Author   | , PhD, MPH;  |

Property of Novartis Confidential May not be used, divulged, published or otherwise disclosed without the consent of Novartis

NIS Protocol Template Primary Data Collection Version 3.0 dated 14-August-2017

## List of abbreviations

| AE     | Adverse Event  |
|--------|--|
| ATC    | Anatomical Therapeutic Chemical  |
| CI     | Confidence Interval  |
| EC     | European Commission  |
| EEA    | European Economic Area   |
| EMA    | European Medicines Agency  |
| ENCePP | European Network of Centres for Pharmacoepidemiology and Pharmacovigilance |
| EU     | European Union   |
| FMV    | Fair Market Value  |
| GPP    | Good Pharmacoepidemiology Practices  |
| GVP    | Good Pharmacovigilance Practices   |
| HCP    | Health Care Professional   |
| ISPE   | International Society for Pharmacoepidemiology                             |
| MAH    | Marketing Authorization Holder   |
| MBC    | Metastatic Breast Cancer   |
| NCA    | National Competent Authority   |
| NIS    | Non-Interventional Study   |
| PASS   | Post-Authorization Safety Study  |
| RMP    | Risk Management Plan   |
| SAP    | Statistical Analysis Plan  |
| SmPC   | Summary of Product Characteristics   |
| SOP    | Standard Operating Procedure   |

#### Title

Survey among healthcare professionals treating patients with metastatic breast cancer in selected European countries to evaluate their knowledge on management of hyperglycemia when using alpelisib

#### Version and date

V00; 08 Jun 2021

#### Name and affiliation of main author

#### Rationale and background

Piqray (alpelisib) is indicated in the EU/EEA in combination with fulvestrant for the treatment of postmenopausal women, and men, with hormone receptor (HR)-positive human epidermal growth factor receptor 2 (HER2)-negative, locally advanced or metastatic breast cancer (MBC) with a PIK3CA mutation after disease progression following endocrine therapy as monotherapy (Novartis 2020). Hyperglycemia is an expected on-target effect of PI3K inhibition (Goncalves et al 2018). To minimise the risk of hyperglycemia, Piqray was approved with a requirement for an additional risk minimization measure using an educational material. Piqray Prescriber's/HCP guide for hyperglycemia was agreed in the Piqray EU RMP v1.3 (dated 19 May 2020), for which EC Decision was granted on 28 May 2020. Specifically, oncologists/healthcare professionals (HCPs) prescribing Piqray in the EU/EEA will be provided with the Piqray Prescriber's/HCP Guide for hyperglycemia (educational material). The educational material aims to provide oncologists/HCPs prescribing Piqray with additional measures/guidance prior to, and during treatment with Piqray for the identification and management of hyperglycemia.

As part of the European Risk Management Plan (RMP) v2.1 (dated 16 Dec 2020) for Piqray, Novartis is required to conduct a Post-authorisation Safety Study (PASS) to assess the effectiveness of the Piqray educational material among HCPs who treat patients with locally advanced or MBC in the EU/EEA. This study is designed and conducted in accordance with Good Pharmacovigilance Practices (GVP) Modules VIII and XVI for a Category 3 PASS.

The PASS utilises a cross-sectional survey study design. In general, only a survey can assess knowledge. Therefore, a survey is considered the optimal methodological approach for this study.

#### **Research question and objectives**

The objective of this survey is to confirm that HCPs received the Piqray educational material and to assess HCPs' knowledge and management of hyperglycemia in patients treated with Piqray.

The primary objective is to assess HCPs' knowledge and understanding of the key information included in the Piqray Prescriber's/HCP Guide for hyperglycemia:

- Risk of hyperglycemia and its potential risk factors
- Signs and symptoms of hyperglycemia
- Recommendations for monitoring for hyperglycemia prior to, and during, treatment with Piqray
- Recommendations for managing hyperglycemia during treatment with Piqray

The primary endpoint is a composite endpoint based on the percentages of HCPs with correct responses to all questions included in the composite regarding the above information.

Secondary objectives are:

 Assess HCPs' reported levels of receipt, and reading, of the Piqray Prescriber's/HCP Guide for hyperglycemia

- Assess HCPs' knowledge levels for each survey question regarding knowledge of, and management of, hyperglycemia
- Assess the primary source from which HCPs learned about the messages included in the Piqray Prescriber's/HCP Guide for hyperglycemia

#### Study design

This is a multinational, non-interventional, cross-sectional survey conducted among HCPs based in the EU/EEA who prescribe Piqray. The survey will assess the knowledge of HCPs prescribing Piqray in relation to the management of hyperglycemia in patients treated with Piqray. The survey will endeavor to collect a minimum to 30-50 completed surveys.

The survey will be conducted in 4 to 8 countries from the EU/EEA. These countries may include Austria, Luxembourg, Norway, Slovenia, Sweden, and the Netherlands plus up to 2 additional countries depending on timing and approval of commercialization of Piqray in additional EU/EEA countries. A sample of HCPs who may/do prescribe Piqray will be recruited from the target population of HCPs who manage care for patients with locally advanced or MBC.

A web-based survey approach will be used to collect data in all selected countries. Information collected will include receipt and reading of the Piqray educational material, and knowledge of key messages included in the Piqray educational materials.

Recruitment will take place a minimum of 6 months following the reimbursement and launch (availability on the market) of Piqray in each participating country.

The survey is anticipated to be open for a minimum of 3 months in each country. Follow-up reminders will be sent to non-respondents to support achieving the target sample size and reducing the impact of selection bias.

#### Setting and study population

The target population is HCPs who were part of the Piqray educational materials dissemination list in any of the participating countries.

#### Variables

The survey questionnaire includes a survey introduction and screening questions to ensure the HCP is eligible to participate in the survey.

#### Outcomes/endpoint variables

Primary endpoint:

- Levels of knowledge of the risk of hyperglycemia, and risk factors for hyperglycemia,
- Levels of knowledge of signs and symptoms of hyperglycemia,
- Levels of knowledge of recommendations for monitoring for hyperglycemia prior to, and during, treatment with Piqray, and
- Levels of knowledge of recommendations for managing hyperglycemia during treatment with Piqray.

The primary endpoint is prescribers' knowledge of the risk of hyperglycemia with Piqray and practices recommended to minimize this risk, expressed as the weighted composite percentage of HCPs with correct responses to the key question set. Success criteria on the primary endpoint is defined as a composite knowledge level of at least 70% across these key questions.

Secondary endpoint questions

- Levels of reported receipt and reading of the Piqray Prescriber's/HCP Guide for hyperglycemia, assessed as the percentages of HCPs who report receipt and reading of the same
- HCPs' knowledge levels for each survey question regarding knowledge of, and management of, hyperglycemia, assessed as the percentages of HCPs with correct responses to each question

 The distribution of responses regarding the primary source from which HCPs learned about the messages included in the Piqray Prescriber's/HCP Guide for hyperglycemia, assessed as the percentages of HCPs who report using each of the possible sources as the primary source they used.

#### Data sources

HCPs will be recruited from the target population of oncologists/HCPs who may prescribe Piqray, and were on the lists for dissemination of the Piqray Prescriber's/HCP Guide for hyperglycemia. If after two reminders the target sample size has not been achieved, the sample may be supplemented through additional outreach based on internet research or outreach through applicable professional societies.

Invitations to participate in the survey will be sent to at least 1000 HCPs by either email (preferred) or by post mail (if email is not available) using the available contact information.

#### Study size

The primary evaluation criteria are prescribers' knowledge of the risk of hyperglycemia with Piqray and practices recommended to minimize this risk, expressed as the weighted composite percentage of HCPs with correct responses to the key question set. The sample size is based on the primary endpoint. With a targeted weighted composite knowledge level of  $\geq$ 70% for the primary endpoint. HCPs allows estimation of a minimum HCP knowledge level of at least 70% with a precision of 9.4%.

#### Data analysis

The primary analysis set will include all HCPs who have completed at least one of the endpoint questions in the survey.

All analyses will be performed using appropriate statistical software (e.g., SAS® Version 9 or later). Data analyses will be descriptive. For continuous variables, counts, means (with standard deviations), medians (with interquartile ranges, minimum, and maximum) will be provided. For categorical variables, frequencies and percentages (with 95% CI) will be provided. Missing data will be reported, but no replacement or imputation will be performed.

Survey administrative details (e.g., the number of invited HCPs, the number and percentage of responding HCPs, the number and percentage of eligible vs. ineligible HCPs, and the number and percentage of HCPs with partially vs. fully completed surveys) and analysis sets will be described overall and by country.

Respondent characteristics/covariates will be summarized overall and by country.

Frequencies, percentages, and corresponding 95% 2-sided CI will be used to summarize the primary and secondary endpoints overall and by country.

For the primary endpoint, the point estimate of the weighted average composite percentage of HCPs who provide correct responses to the key question set will be estimated and assessed against the 70% threshold.

#### Milestones

Planned dates of study milestones:

Start date of data collection: October 2021

Last date of data collection: October 2022

Submission of final report of study results: 30 April 2023

## 3 Amendments and updates

#### 4 Milestones

| Table 4-1Planned dates of study milestor | nes |
|--|-----|
|--|-----|

| Milestone                                   | Planned date                      |
|---|-----------------------------------|
| Registration in the EU PASS register        | Prior to start of data collection |
| Start of data collection                    | October 2021                      |
| End of data collection                      | 31 Oct 2022                       |
| Submission of final report of study results | 30 April 2023                     |

## 5 Rationale and background

Pigray (alpelisib) is an orally administered alpha specific PI3K inhibitor indicated in the EU/EEA in combination with fulvestrant for the treatment of postmenopausal women, and men, with hormone receptor (HR)-positive human epidermal growth factor receptor 2 (HER2)negative, locally advanced or metastatic breast cancer (MBC) with a PIK3CA mutation after disease progression following endocrine therapy as monotherapy (Novartis, 2020). Hyperglycemia is an expected on-target effect of PI3K inhibition since targeting p110a can block glucose uptake into skeletal muscle and adipose tissue, resulting in hyperglycemia (Goncalves et al 2018). To minimise the risk of hyperglycemia (including life-threatening and fatal events), Pigray was approved with a requirement for additional risk minimization measure using an educational material. Pigray Prescriber's/HCP guide for hyperglycemia was agreed in the Pigray EU RMP v1.3 (dated 19 May 2020), for which EC Decision was granted on 28 May 2020. Specifically, oncologists/healthcare professionals (HCPs) prescribing Piqray in the EU/EEA will be provided with the Pigray Prescriber's/HCP Guide for hyperglycemia (educational material), as agreed in the Pigray European Risk Management Plan (RMP), version 1.3 (dated 19.May.2020). The educational material aims to provide oncologists/HCPs prescribing Piqray with additional measures/guidance prior to, and during, treatment with Piqray, for the identification and management of hyperglycemia.

As part of the European Risk Management Plan (RMP) for Piqray, Novartis is required to conduct a Post-authorisation Safety Study (PASS) to assess the effectiveness of the Piqray educational materials among HCPs who treat patients with locally advanced or MBC in the EU/EEA. After Novartis has obtained approval of the educational materials from each concerned National Competent Authority (NCA) where Piqray will be commercialized and has disseminated these educational materials, this PASS will be conducted to assess the effectiveness of the Piqray educational materials among HCPs who prescribe Piqray in the EU/EEA. This study will be designed and conducted in accordance with Good Pharmacovigilance Practices (GVP) Modules VIII and XVI for a Category 3 PASS.

The PASS utilises a cross-sectional survey study design. In general, only a survey can assess knowledge. Therefore, a survey is considered the optimal methodological approach for understanding prescribers' knowledge of safe-use conditions for treating patients with Piqray.

Surveys are an accepted methodology to evaluate knowledge of educational materials and are referenced as an appropriate tool in Module XVI of GVP.

## 6 Research question and objectives

The objective of this survey, amongst oncologists/HCPs prescribing Piqray in selected countries in the EU/EEA, is to confirm that they received the educational material and to assess their knowledge, understanding and management of hyperglycemia in patients treated with Piqray.

Assessing, firstly, the dissemination of the educational material, and upon receipt of the material assess prescribing physicians' knowledge, understanding and behavior relating to the management of hyperglycemia as detailed in the educational material and SmPC provided. The educational material provides additional guidance to the SmPC, for prior to and during treatment with Piqray, on the management of hyperglycemia, particularly focusing on testing fasting glucose (FG) and HbA1c, and optimizing blood glucose levels prior to treatment initiation; monitoring FG and HbA1c during treatment; and management of hyperglycemia if it occurs.

## 6.1 **Primary objective**

Assess HCPs' knowledge of the key information included in the Piqray Prescriber's/HCP Guide for hyperglycemia:

- Risk of, and risk factors for, hyperglycemia
- Signs and symptoms of hyperglycemia
- Recommendations for monitoring for hyperglycemia prior to, and during, treatment with Piqray
- Recommendations for managing hyperglycemia during treatment with Piqray

The primary endpoint is a composite endpoint based on the percentages of HCPs with correct responses to all questions included in the composite regarding the above information

## 6.2 Secondary objectives

[figure not shown]
- Assess HCPs' reported levels of receipt, and reading, of the Piqray Prescriber's/HCP Guide for hyperglycemia
- Assess HCPs' knowledge levels for each survey question regarding knowledge of, and management of, hyperglycemia
- Assess the primary source from which HCPs learned about the messages included in the Piqray Prescriber's/HCP Guide for hyperglycemia

## 7 Research methods

## 7.1 Study design

Figure 7-1 provides a study flow chart.

#### Figure 7-1 Study flow chart

This is a multinational, non-interventional, cross-sectional survey to evaluate the effectiveness of the educational materials for Piqray. The survey will be conducted among HCPs based in the EU/EEA who prescribe Piqray. The survey will assess the knowledge of HCPs prescribing Piqray in relation to the management of hyperglycemia in patients treated with Piqray. The survey will endeavor to collect a minimum of 30 to 50 completed surveys.

The PASS will be conducted in 4 to 8 countries from the EU/EEA. This includes 6 countries where Piqray is planned to be reimbursed and commercially available within 1 year of Piqray's centralized marketing authorization approval on 27 July 2020 (European Commission [EC] decision date); specifically, Austria, Luxembourg, Norway, Slovenia, Sweden, and the Netherlands. Up to 2 additional countries may be included, depending on the timing and approval of commercialization of Piqray in additional EU/EEA countries relative to the survey study milestones and requirements. A sample of HCPs who may/do prescribe Piqray will be recruited from the target population of HCPs who manage care for patients with locally advanced or MBC. The final list of countries will also consider geography and market share (for example, small countries with only a few HCPs prescribing Piqray may be excluded).

Confidential

A web-based survey approach will be used to collect data in all selected countries. Information collected will include receipt and reading of the Piqray educational material, and knowledge of key messages included in the Piqray educational materials.

Recruitment will take place a minimum of 6 months following the reimbursement and launch (availability on the market) of Piqray in each participating country. Since Piqray launch will be staggered, the intention is to implement the survey at different times depending on each country's reimbursement date, but at a fixed period after each country's launch. This reduces the chance of any bias introduced by some HCPs prescribing Piqray having longer or shorter durations of experience with the Piqray.

The survey is anticipated to be open for a minimum of 3 months in each country. Follow-up reminders will be sent to non-respondents to support achieving the target sample size and reducing the impact of selection bias.

## 7.2 Setting

The target population is HCPs who were part of the Piqray educational materials dissemination list in any of the participating countries.

The target groups for dissemination of the Piqray educational material were established by Novartis, as agreed with each NCA, and as outlined in Annex IID are HCPs who manage care for patients with locally advanced or MBC and may intend to prescribe Piqray.

## 7.2.1 Inclusion criteria

- Has prescribed Piqray to at least 1 locally advanced or MBC patient within 6 months prior to completing the survey.
- Provides permission to share their anonymized responses in aggregate with EMA or NCAs, if requested.

## 7.2.2 Exclusion criteria

HCPs who are direct employees of Novartis, the EMA (or any other regulatory bodies), or

#### 7.3 Variables

Novartis

The survey questionnaire includes a survey introduction and screening questions to ensure the HCP is eligible to participate in the survey. The main survey questions are described in Sections 7.3.1 through 7.3.3, and Table 7-1.

#### 7.3.1 **Outcomes/endpoint variables**

Primary endpoint:

- Levels of knowledge of the risk for hyperglycemia, and risk factors for hyperglycemia, (survey question 4A, 6),
- Levels of knowledge of signs and symptoms of hyperglycemia (survey questions 5A-C), •
- Levels of knowledge of recommendations for monitoring for hyperglycemia prior to, and during, treatment with Pigray (survey questions 8A-C, 10, 15) and
- Levels of knowledge of recommendations for managing hyperglycemia during treatment ٠ with Piqray (survey questions 12-14).

The primary endpoint is a composite endpoint that combines correct responses given by HCPs to questions included in the composite. Specifically, the primary endpoint is a weighted composite knowledge score aggregated across the following survey questions: 4A, 5A-C, 6, 8A-C. 10, and 12-15. It is calculated as the number of all correctly answered questions divided by the number of all answered questions (i.e. questions that were answered either correct and not correct – unanswered questions are excluded).

Success criteria on the primary endpoint is defined as a weighted composite knowledge level of at least 70% across these key questions.

Secondary endpoint questions:

- Levels of reported receipt and reading of the Pigray Prescriber's/HCP Guide for • hyperglycemia, assessed as the percentages of HCPs who report receipt and reading of the same (survey questions 1, 2)
- HCPs' knowledge levels for each survey question regarding knowledge of, and • management of, hyperglycemia, assessed as the percentages of HCPs with correct responses to each question (individual responses to survey questions 4-15)
- The distribution of responses regarding the primary source from which HCPs learned • about the messages included in the Piqray Prescriber's/HCP Guide for Hyperglycemia, assessed as the percentages of HCPs who report using each of the possible sources as the primary source they used (survey question 3).

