#### Table 7-1Outcomes/endpoints collected in the survey

| Study objective domains assessed   | Corresponding variable (original data collected;
all are categorical variables)  | Operational
definition/derivation
"Calculated as the
percentage of HCPs
who" |
|--|---|--|
| HCPs' knowledge of the risk for hyperglycemia and                                      | Knowledge that hyperglycemia is a risk associated with treatment with Piqray (key question)   | "Checked" question 4A  |
| risk factors for
hyperglycemia  | Knowledge that pneumonitis is a risk associated with treatment with Piqray  | "Checked" question 4B  |
|  | Knowledge that severe cutaneous reactions are a risk associated with treatment with Piqray  | "Checked" question 4C  |
|  | Knowledge that suicidal ideation is not a risk associated with treatment with Piqray  | "Not checked" question
4D   |
|  | Knowledge that onychomycosis is not a risk associated with treatment with Piqray  | "Not checked" question 4E  |
|  | Knowledge that being diabetic/pre-diabetic, having a fasting blood glucose >13.9 mmol/L( 250 mg/dL), and being 75 years of age or older are additional risk factors for developing hyperglycemia while taking Piqray (key question) | "Checked" only "body
mass index <30
kg/m  "for question 6              |
| HCPs' knowledge of the
signs and symptoms of  | Knowledge that excessive thirst is a sign/symptom of hyperglycemia (key question)   | "Checked" question 5A  |
| hyperglycemia  | Knowledge that increased frequency or amount of urination is a sign/symptom of hyperglycemia (key question)   | "Checked" question 5B  |
|  | Knowledge that increased appetite with weight loss is a sign/symptom of hyperglycemia (key question)  | "Checked" question 5C  |
|  | Knowledge that inability to swallow is not a sign/symptom of hyperglycemia  | "Not checked" question 5D  |
|  | Knowledge that yellowing of the skin is not a
sign/symptom of hyperglycemia  | "Not checked" question 5E  |
|  | Knowledge that difficulty breathing is a sign/symptom of hyperglycemia (key question)   | "Checked" question 5F  |
|  | Knowledge that nausea and/or vomiting is a sign/symptom of hyperglycemia (key question)   | "Checked" question 5G  |
|  | Knowledge that headache is a sign/symptom of hyperglycemia (key question)   | "Checked" question 5H  |

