## 13 Appendices

## 13.1 Appendix – HCP Survey questionnaire

#### SURVEY QUESTIONNAIRE

Note to Reviewers:

- 1. Items in **RED** font are programming instructions and will not be seen by HCPs who complete the survey.
- 2. Items in *italics* are information for questionnaire reviewers and will also not be seen by HCPs who complete the survey.

Please enter your Unique ID to participate in the survey. Your Unique ID was provided in your survey invitation.

Unique ID: \_\_\_\_\_ → IF ENTERED, PROCEED TO COUNTRY AND LANGUAGE SELECTION, OTHERWISE, TERMINATE SURVEY

The above section will only appear for respondents who did not receive their invitation directly by email from the survey software.

Surveys sent by post will include a unique ID in their invitation letter, which will need to be entered.

Correct responses are ticked as  $\checkmark$  and will be removed for the versions used for pre-testing and the actual survey.

Key questions for the primary endpoint are noted in brackets.

Please select your country and preferred language from the list below:

| □ Country 1 (language or English) | → PROCEED TO SURVEY INTRODUCTION |
|-----------------------------------|----------------------------------|
| Country 2 (language or English)   | → PROCEED TO SURVEY INTRODUCTION |
| Country 3 (language or English)   | → PROCEED TO SURVEY INTRODUCTION |
| □ Country 4 (language or English) | ➔ PROCEED TO SURVEY INTRODUCTION |
| Country 5 (language or English)   | → PROCEED TO SURVEY INTRODUCTION |
| □ Country 6 (language or English) | → PROCEED TO SURVEY INTRODUCTION |
| □ My country is not listed        | ➔ THANK AND TERMINATE            |
|                                   |                                  |

[Termination Language for Non-Qualified Candidates:]

Once country/language is selected, the survey introduction is displayed in local language (next page).

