#### [ON-LINE SURVEY - PROGRAMMER: RANDOMIZE THE ORDER OF THESE 5 QUESTIONS]

5. Hyperglycemia is a reversible, on target effect of treatment with Piqray. Which of the following signs and symptoms should patients be counselled about to help identify and mitigate the risk of hyperglycemia? (check all that apply)

|   |   | Sign/symptom of
hyperglycemia |
|---|---|----------------------------------|
| А | Excessive thirst [KEY QUESTION]                           | 1                                |
| В | Increased frequency or amount of urination [KEY QUESTION] | ~                                |
| С | Increased appetite with weight loss
[KEY QUESTION]     | 1                                |
| D | Inability to swallow                                      |                                  |
| E | Yellowing of the skin                                     |                                  |
| F | Difficulty breathing [KEY QUESTION]                       | ~                                |
| G | Nausea and/or vomiting [KEY QUESTION]                     | 1                                |
| Η | Headache [KEY QUESTION]                                   | 1                                |
| Ι | I don't know/am not sure                                  |                                  |

[ON-LINE SURVEY - PROGRAMMER: RANDOMIZE THE ORDER OF THESE 8 QUESTIONS] 6. Which of the following is NOT a risk factor for patients to develop hyperglycemia when receiving treatment with Piqray?

□ Diabetic or pre-diabetic
 □ Fasting glucose >250 mg/dL (13.9 mmol/L)
 ✓ Body mass index <30 kg/m^2
 □ Age ≥75 years
 □ I don't know/am not sure

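### The primary composite has two item lists: 13 items in Section 7.3.1, but 16 in Table 7-1, which adds 5F, 5G and 5H as the questionnaire also does; the 70% verdict can depend on which is used.

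*Protocol*

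**What the plan says.** **Section 7.3.1** gives the item set twice. The four domain bullets assign 4A and 6 to risk and risk factors, 5A-C to signs and symptoms ("Levels of knowledge of signs and symptoms of hyperglycemia (survey questions 5A-C")), 8A-C, 10 and 15 to monitoring, and 12-14 to management. The sentence defining the score then says it is "aggregated across the following survey questions: 4A, 5A-C, 6, 8A-C. 10, and 12-15". The score is correct answers divided by answered questions over that set, and success is 70% or more.

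**Table 7-1** labels every one of those items as a key question and adds three:
- 5F: "Knowledge that difficulty breathing is a sign/symptom of hyperglycemia (key question")
- 5G: "Knowledge that nausea and/or vomiting is a sign/symptom of hyperglycemia (key question")
- 5H: "Knowledge that headache is a sign/symptom of hyperglycemia (key question")

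**Appendix 13.1** explains its tagging convention: "Key questions for the primary endpoint are noted in brackets". Under question 5 the tag stands on 5A-C and also on 5F-H, for example "Difficulty breathing [KEY QUESTION"] and "Nausea and/or vomiting [KEY QUESTION"].

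**Section 7.7.2** (planned analyses) compares the point estimate of the composite with the 70% threshold.

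**The concern.** The item list is the definition of the primary endpoint. It fixes the numerator, the denominator and the weight of each knowledge domain. Here the defining text excludes three items, while the table that operationalises the outcomes and the data collection instrument both include them.

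The protocol does not defer the list to the SAP; it states it, in two incompatible forms. Under Section 7.7 the SAP need only be final before database close, so the choice could be made after responses have come in. The verdict is a comparison of a point estimate with 70%, so no confidence bound absorbs a shift caused by the choice of list.

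**Working it through.** **The plan's own figures.** The protocol states no total number of key items. Its stated precision at a 70% knowledge level (Section 7.5, Table 7-4) reproduces with the Clopper-Pearson interval:
- n = 30: 50.6% to 85.3%, half-width 17.3 points (stated 17.4)
- n = 50: 55.4% to 82.1%, half-width 13.4 points (stated 13.4)

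These figures treat the score as one proportion per respondent and do not depend on the number of items.

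**Step 1: count the items.** No item in the text list is missing from the table. The difference is exactly 5F, 5G and 5H.

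| Domain | Section 7.3.1 | Table 7-1 labels | Share of 13 | Share of 16 |
|---|---|---|---|---|
| Risk and risk factors | 4A, 6 (2) | 4A, 6 (2) | 15.4% | 12.5% |
| Signs and symptoms | 5A-C (3) | 5A-C, 5F-H (6) | 23.1% | 37.5% |
| Monitoring | 8A-C, 10, 15 (5) | 8A-C, 10, 15 (5) | 38.5% | 31.3% |
| Management | 12-14 (3) | 12-14 (3) | 23.1% | 18.8% |
| Total | 13 | 16 | | |

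**Step 2: the pass mark if every item is answered.**
- n = 30: 0.70 × 390 = 273 correct on 13 items; 0.70 × 480 = 336 on 16
- n = 50: 0.70 × 650 = 455 correct on 13 items; 0.70 × 800 = 560 on 16

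**Step 3: the relation between the two scores.** Let s be the 13-item score and q the average correct rate on 5F-H, with all items answered. Then

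S16 = (13s + 3q) / 16.

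The protocol gives neither s nor q, so the values below are assumptions.
- s = 72%, q = 45%: (9.36 + 1.35)/16 = 66.9%. Pass on 13 items, fail on 16.
- s = 65%, q = 100%: (8.45 + 3.00)/16 = 71.6%. Fail on 13 items, pass on 16.

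**Step 4: break-even.** S16 reaches 70% when q = (16 × 0.70 − 13s)/3 = (11.2 − 13s)/3.

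| s | q needed for S16 = 70% |
|---|---|
| 65% | 91.7% |
| 70% | 70.0% |
| 72% | 61.3% |
| 75% | 48.3% |
| 80% | 26.7% |
| 85% | 5.0% |

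**Step 5: where the verdicts can differ at all.** With q = 0, S16 = 70% at s = 11.2/13 = 86.2%. With q = 1, S16 = 70% at s = (11.2 − 3)/13 = 63.1%. Outside 63.1% to 86.2% both lists give the same verdict whatever q is.

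**The case against.** **Section 7.3.1 could be taken as operative.** It holds the only formal definition of the composite and agrees with itself, whereas the derivation column of Table 7-1 defines per-item percentages. That is a reasonable argument, but the protocol states no such precedence, and the questionnaire expressly ties its tags to the primary endpoint.

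**The consequence is recoverable.** Items 5F-H are collected and reported individually as secondary endpoints under either list, so both scores can be computed from the same data. This is true and makes the fix cheap. It does not say which score decides success.

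**The shift is small against the precision.** The 72% example moves by 5.1 points, less than the 13.4 to 17.4 points stated for 50 to 30 respondents, and the analysis is descriptive. But success is read off the point estimate, so the interval width does not protect the verdict.

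**Two stronger readings are not supported.** A reader might infer a third list from the questionnaire, because its converted text shows the tag on only nine items (4A, 5A-C, 5F-H, 14 and 15). That stretch has visibly lost content: questions 11 and 13 show no tick although Table 7-1 gives their correct answers, and some question numbers are gone. The missing tags may be lost in the same way. A reader might also infer that 5F-H are less typical symptoms, would be answered less well, and so would lower the score. The protocol has no expected correct rate for any item, so no direction can be claimed.

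**Conclusion.** The contradiction stands. The defining text uses 13 items, the table labels 16, the questionnaire agrees with the table on 5F-H, and nothing resolves it. The counts and the change in symptom weight (23.1% to 37.5%) are exact.

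The effect on the verdict is a possibility, not a forecast. It rests on assumed correct rates and on all items being answered, can go either way, and arises only for a 13-item score between about 63% and 86%. That range contains the protocol's own 70% target, and near the target it takes little: at s = 72%, any 5F-H average below 61.3% reverses a pass. At s = 85% the average would have to be below 5%. The sample-size and precision figures are unaffected. Because the point concerns the definition of the primary endpoint, it should be settled before launch.

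**What to change.** Before data collection starts, choose one key-item list and make four places identical: the domain bullets in Section 7.3.1, the defining sentence in 7.3.1, the labels in Table 7-1, and the tags in Appendix 13.1.
- If the 13-item set is intended, remove the key label from 5F, 5G and 5H in the table and the questionnaire.
- If the 16-item set is intended, change 5A-C to 5A-C and 5F-H in both places in 7.3.1.

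Check at the same time that the source questionnaire carries the tag on every item of the chosen list.

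The score on the other set may be reported as an optional sensitivity analysis. The cost is a wording correction: no question is added or dropped, and neither the sample size nor the data collected changes.
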